1. INTRODUCTION

This Statistical Analysis Plan (SAP) is to describe the planned analyses to be included in the clinical study report (CSR) for VIR-SHB1-V201 (STRIVE). The following documents were reviewed in preparation for this SAP:

- Master Protocol VIR-MHB1-V200 (PREVAIL), Amendment 2, 11Oct2022, Version 3.0
- Sub-study Protocol VIR-SHB1-V201 (STRIVE), Amendment 3, 14Dec2023, Version 1.0
- Electronic case report form (eCRF), Version 5 and eCRF completion guidelines (CCG).

This SAP documents the planned statistical analyses of efficacy, safety and tolerability, pharmacokinetic (PK) endpoints and immunogenicity endpoints for the interim analyses (IAs) and the final analysis of Study VIR-SHB1-V201 (STRIVE) data. In addition, some exploratory endpoint analyses may be documented in this SAP as well to provide supportive information for the scientific understanding of the study intervention entity.

The VIR Biometrics team and a designated contract research organization (CRO) will perform the statistical analysis.

This SAP will be finalized and approved prior to the first Interim Analysis (IA) data cutoff date. Any revisions to the approved SAP will be documented and approved in an amendment to the SAP. Important changes to the SAP after the database lock for the final analysis, along with justifications for the changes, will be described in the CSR. Changes to the protocol will require an SAP amendment ONLY if the changes are to a principal feature of the protocol. Any post hoc or unplanned analyses that are performed and not specifically specified in this SAP will be clearly identified as such if they are included in the CSR.

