4. STATISTICAL ANALYSES

4.1. General Considerations

All analyses will use SAS version 9.4 or higher. The schedule of study assessments and time points are provided in the current PREVAIL master protocol and STRIVE sub-study.

Data will be provided in by-participant listings for the All Enrolled Set, unless otherwise specified.

Efficacy endpoints will be summarized by TDF/TD discontinued (participants who discontinued TDF/TD when the TDF/TD discontinuation criteria were met in the Follow-up period) and overall for each cohort.

Continuous variables will be summarized using the following descriptive summary statistics: the number of participants (n), mean, standard deviation (SD), median, Q1 (first quartile), Q3 (third quartile), minimum value (min), and maximum value (max), unless otherwise specified. In general, the precision of the measurement for each continuous variable will be used to determine the number of decimal places to present in tables, figures, and derived listings. Minimum and maximum values will be reported with the same precision as the units of measure. The mean and median will be reported to 1 additional decimal place, and the SD will be reported to 2 additional decimal places. Any values that require transformation to standard units (metric or SI) will be converted with the appropriate corresponding precision.

Categorical variables will be summarized using counts and percentages. Percentages will be rounded to one decimal place, except 100% will be displayed without any decimal places, and percentages will not be displayed for zero counts.

Baseline value: Unless otherwise specified, the baseline value will be defined as the most recent non-missing (scheduled or unscheduled) measurement collected prior to the initial administration of study intervention. If baseline cannot be determined due to missing data, no derivation will be performed, and baseline will be set to missing.

Change (absolute change) from baseline will be calculated as post-baseline value – baseline value.

Study day: The study day of an event/measurement is defined as the relative day of the event/measurement starting with the date of the first study drug administration (reference date) as Day 1 (there will be no Day 0).

The study day of event/measurement occurring before the first study drug administration will be calculated as:

$$\text{Study Day} = (\text{Date of event/measurement} - \text{Date of first study drug administration})$$

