- For efficacy response variables, the missing equals failure (MEF) approach will be used for the analysis, except for the sensitivity analysis for the primary endpoint described in [Section Error! Reference source not found.](#). The sensitivity analysis will be conducted to evaluate the impact of missing data, in which missing data will be imputed.
- Missing data will not be imputed, and will be considered as missing data that will not be included in the data summary statistics and analysis. Qualitative data will be imputed as follows:
 1. HBV DNA, for the analysis of the primary endpoint:

- a. If the missing data is reported as “Target Not Detected (TND)”, then the missing data point will be imputed as 0.
- b. If the missing data is reported as “< LLOQ”, then the missing data point will be imputed 1 unit less than the LLOQ value. That’s the LLOQ for HBV DNA is 20 IU/mL, so 19 IU/mL will be imputed.

2. HBs(e)Ag and Anti-HBs(e), for the analyses of primary and secondary efficacy endpoints:
If the missing data is reported as “Not Detected” or “Nonactive”, then the missing data point will be imputed as 0.
3. HBV RNA, for the analysis of an exploratory endpoint:
 - a. If the missing data is reported as “Not Detected”, then the missing data point will be imputed as 0.
 - b. If the missing data is reported as “< LLOQ”, then the missing data point will be imputed 1 unit less than the LLOQ value. That’s the LLOQ for HBV RNA is 0.49 log U/mL, so 0.48 log U/mL will be imputed.
 - c. If the missing data is reported as “> upper limit of quantification (ULOQ)”, then the missing data point will be imputed as 1 unit greater than the value of ULOQ. E.g., The ULOQ for HBV RNA is 6.0 log U/mL, so 6.1 log U/mL will be imputed.
 - d. If the missing data is reported as “Invalid” or “Quantity Not Sufficient (QNS)”, then the missing data will not be imputed and considered as missing data.
4. HBcrAg, for the analysis of an exploratory endpoint:
 - a. If the missing data is reported as “TND”, then the missing data point will be imputed as 0.
 - b. If the missing data is reported as “Target Detected (TD)”, then the missing data point will be imputed as 1 unit less than the LLOQ. That’s the LLOQ is $3.0 \log_{10} \text{U/mL}$, so $2.9 \log_{10} \text{U/mL}$ will be imputed.

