 - c. If the missing data is reported as “> ULOQ”, then the missing data point will be imputed as 1 unit greater than the value of ULOQ. That’s, the ULOQ for HBcrAg, depending on whether the dilution could be performed, is either $7.0 \log_{10} \text{U/mL}$ or $9.0 \log_{10} \text{U/mL}$, then $7.1 \log_{10} \text{U/mL}$ or $9.1 \log_{10} \text{U/mL}$ will be imputed, respectively.
 - d. If the missing data is reported as “QNS” or “Results pending”, then the missing data point will not be imputed, and it is considered as a missing.
5. In case other viral parameters are reported in a similar way, the same rule is applied if applicable.
6. For laboratory parameters, the below imputation rule will be applied: if any laboratory parameters are reported outside the reportable range (i.e. “< minimum reportable value (minRV)” or “> maximum reportable value (maxRV)”), one unit less than the minimum reportable value and one unit greater than the maximum reportable value will be imputed, respectively. For example, if the reported results is “< 0.05”, then 0.04 will be imputed; if the reported results is “> 0.3”, then 0.4 will be imputed. For special reported values, e.g. < 1 or < 0.1 will be imputed as < 0.9 or < 0.09, respectively. The lab data with a value of $\leq x.x / \geq x.x$ will be imputed by x.x.

7. For the summary of medication and adverse event, no imputation will be performed except for missing/partial dates. The imputation rules for missing/partial dates of medication and adverse event are specified in [Section 4.2.4](#) and [Section 4.7.3](#), respectively.

Outliers: No formal statistical analysis will be performed to detect and/or remedy the presence of statistical outliers.

Laboratory data analysis scope: For laboratory parameters, only data from the central lab will be analyzed and summarized. Local laboratory data will not be analyzed or summarized but will be provided in a by-participant laboratory data listing, with a flag indicating the data is from the local lab.

Multicenter considerations: Data from different sites will be pooled for analysis.

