4.5. Exploratory Endpoints Analysis

4.5.1. Exploratory Efficacy Analysis

The analyses of the following exploratory efficacy endpoints will be conducted based on the FAS, unless otherwise specified. The numbering in the table below is consistent with the numbering of the endpoints in [Table 1](#). HBV RNA and HBcrAg values will be provided in a by-participant listing.

[figure not shown]
Exploratory Endpoints	Analysis Methods
1. Additional viral parameters associated with HBV and/or study intervention(s), including but not limited to HBV RNA and HBcrAg	
The observed values and the absolute change from baseline values at each visit up to End of Follow-up will be summarized using descriptive statistics (n, mean, SD, median, Q1, Q3, min, max) by cohort for the following HBV viral parameters:
 
 • HBV RNA in \log_{10} U/mL • HBcrAg in \log_{10} U/mL

Exploratory Endpoints	Analysis Methods
2. CCI	CCI
3. CCI	CCI
4. Emergence of viral resistance to study intervention(s)	Not covered by this SAP, will be analyzed separately.
7. For HBeAg-positive participants: time to achieve HBeAg loss (undetectable HBeAg) and/or anti-HBe seroconversion	Time to HBeAg loss and/or anti-HBe seroconversion will be summarized as a continuous variable. Participants with HBeAg loss with or without anti-HBe seroconversion will be listed.
8. Proportion of participants meeting criteria for NRTI discontinuation or retreatment in the study	The number and percentage of participants who meet NRTI discontinuation criteria NRTI retreatment criteria will be summarized by cohort. A by-participant listing will be provided for participants who met NRTI discontinuation criteria and retreatment criteria.
9. HBV DNA levels and change from baseline across timepoints in the study 10. Nadir and maximum change of HBV DNA level from baseline in the study	The observed values and the absolute change from baseline values of HBV DNA in both log IU/mL and IU/mL: a. at each visit b. at nadir up to EOS, will be summarized using descriptive statistics (n, mean, SD, median, Q1, Q3, min, max) by cohort. In addition, the change from baseline in \log_{10} IU/mL and absolute value in \log_{10} IU/mL at

Exploratory Endpoints	Analysis Methods
	each visit will be plotted for each participant by cohort.

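### The STRIVE SAP's two upper limits for HBcrAg can put up to 2.0 log10 of assay artefact into the exploratory change from baseline if a participant's dilution status differs between visits

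*SAP*

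**What the plan says.** The SAP supplied is the plan for STRIVE. Its introduction names "Sub-study Protocol VIR-SHB1-V201 (STRIVE), Amendment 3, 14Dec2023, Version 1.0" as the sub-study protocol reviewed. The protocol supplied is that of a different sub-study, THRIVE, so this point concerns the STRIVE plan.

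SAP 4.1 has a rule headed "HBcrAg, for the analysis of an exploratory endpoint". For a result reported as above the upper limit of quantification (ULOQ), "then the missing data point will be imputed as 1 unit greater than the value of ULOQ". The rule adds that "the ULOQ for HBcrAg, depending on whether the dilution could be performed, is either" 7.0 or 9.0 log10 U/mL, and it gives the replacement values as 7.1 and 9.1.

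The same section defines change: "Change (absolute change) from baseline will be calculated as post-baseline value" minus the baseline value. SAP 4.5.1 applies this to HBcrAg under exploratory endpoint 1: "The observed values and the absolute change from baseline values at each visit up to End of Follow-up will be summarized using descriptive statistics", by cohort and in log10 U/mL. Interim analysis 1 uses the same summary (SAP 4.9.3.5.3).

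The supplied text does not require one upper limit within a participant. It also has no flag for dilution status, no count of over-range results and no sensitivity analysis for pairs measured under different limits.

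**The concern.** The rule lets one true HBcrAg level be recorded as two different numbers, according to how the sample was handled. A true 8.5 is recorded as 7.1 undiluted and as 8.5 diluted. When the two samples of a change score were handled differently, the gap between the numbers enters the change score as if it were biology. A diluted baseline with an undiluted later sample gives a false fall, which looks like response to treatment. The reverse order gives a false rise.

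The rule's wording makes dilution depend on whether it was feasible, which reads as a contingency of the sample. The same list allows quantity not sufficient as an HBcrAg result, so a volume limit is a plausible reason, although the SAP does not state one.

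At stake is the reading of the HBcrAg mean change in cohorts of about 10 (1a, 2a, 3a) or 15 (4a, 5a) (SAP 1.2.2), where a single participant has visible weight.

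**Working it through.** **Inputs.** ULOQ 7.0 or 9.0 log10 U/mL, replacement values 7.1 or 9.1, and change as post-baseline minus baseline (all SAP 4.1). Cohort sizes of about 10 or 15 (SAP 1.2.2).

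**The plan's own figures.** 7.0 + 0.1 = 7.1 and 9.0 + 0.1 = 9.1, so both replacement values reproduce with a step of 0.1 log10. The SAP calls this step one unit. Read literally as 1 log10, it would give 8.0 and 10.0, which contradicts the SAP's stated values. The two over-range values would still differ by 10.0 - 8.0 = 2.0.

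**Artefact for an unchanged true level t.** The recorded value is t if t is at or below the ULOQ, and ULOQ + 0.1 otherwise. The artefact is the recorded value under ULOQ 9.0 minus the recorded value under ULOQ 7.0.

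| True level t | Recorded, undiluted | Recorded, diluted | Artefact |
|---|---|---|---|
| 6.9 | 6.9 | 6.9 | 0.0 |
| 7.5 | 7.1 | 7.5 | 0.4 |
| 8.0 | 7.1 | 8.0 | 0.9 |
| 8.5 | 7.1 | 8.5 | 1.4 |
| 9.0 | 7.1 | 9.0 | 1.9 |
| above 9.0 | 7.1 | 9.1 | 2.0 |

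The maximum is 9.1 - 7.1 = 2.0, reached when both results are over range. The figure of 1.9 (9.0 - 7.1) applies when the diluted result is still quantified at 9.0. The sign of the error in the change score depends on which sample was diluted.

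**Effect on a cohort mean change.** The shift is artefact × k / n for k affected participants, all in the same direction.

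- n = 10, k = 1: 2.0 / 10 = 0.20 (1.4 / 10 = 0.14 for a constant 8.5).
- n = 15, k = 1: 2.0 / 15 = 0.13.
- n = 10, k = 3: 6.0 / 10 = 0.60. n = 15, k = 3: 6.0 / 15 = 0.40.

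The values of k are illustrative, because the documents give no frequency.

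**A true decline.** Two participants both fall from 8.5 to 6.5. With a diluted baseline the change is 6.5 - 8.5 = -2.0; with an undiluted baseline it is 6.5 - 7.1 = -0.6. The later value needs no dilution. The same course therefore enters the same mean as two changes that are 1.4 apart.

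**Check of a common ceiling.** If every result above 7.0 is recorded as 7.1 whatever its dilution status, the artefact is 0.0 at every true level. Both participants in the last example are then recorded as -0.6.

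**The case against.** The strongest objection is that the mechanism is inferred. A reader might take the SAP to say that dilution status varies between visits of the same participant. It says only that the limit depends on whether dilution could be performed; status could be constant within a participant, laboratory or period. If it is constant within a participant, an unchanged level shows no false change, and what remains is ordinary loss of information above the ceiling. A laboratory manual or the STRIVE protocol may settle this, and neither was supplied. This objection stands, and the conclusion is conditional for that reason.

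A reader might also infer that over-range values cluster at baseline, because STRIVE enrols participants without prior NRTI or PEG-IFNα and with HBV DNA above 2,000 IU/mL (SAP 1.2.1). That is plausible, but neither document gives any HBcrAg distribution.

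The consequence is limited too. HBcrAg is exploratory, the study tests no hypothesis (SAP 2), and SAP 4.5.1 also reports medians and quartiles and lists HBcrAg values by participant. A median resists a few discordant values. This lowers the severity but does not remove the point: the mean is also a planned summary, and a listing without a dilution flag does not show which changes are affected.

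**Conclusion.** The point holds, conditionally and as a minor one. As written, the rule can create a false change in HBcrAg of up to 2.0 log10 for one participant, and can shift a cohort mean change by up to 0.20 at n = 10 or 0.13 at n = 15 for each participant affected. This requires a true level above 7.0 and, for a false change at a constant level, different dilution status at the two visits. How often either occurs is not stated.

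Three wider readings are not supported:

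- **Effect on the main results.** The primary endpoint uses HBV DNA and HBsAg (SAP 4.3.1), and no secondary endpoint uses HBcrAg (SAP 4.4.1). None of them is affected.
- **The same fault in HBV RNA.** SAP 4.1 gives that assay a single upper limit, 6.0 log U/mL, so there is no dilution switch.
- **A consequence for THRIVE.** The rule is in the STRIVE SAP, and applying it to THRIVE would be an assumption.

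**What to change.** Keep the HBcrAg over-range rule in SAP 4.1 for the main summary and add two items to SAP 4.5.1, endpoint 1:

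1. Report the number of HBcrAg results above 7.0 log10 U/mL by visit, cohort and dilution status, and flag dilution status in the by-participant listing.
2. Add a supportive change-from-baseline summary in which every HBcrAg result above 7.0, diluted or not, is set to one common ceiling value at all visits. The value 7.1, already used for the lower limit, would serve.

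The cost is SAP wording and programming, provided that dilution status is available from the laboratory data. The downside is that a common ceiling hides true change above 7.0, so the supportive summary belongs beside the main one and should not replace it.

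Leaving out every change that involves an undiluted over-range result would be a poorer choice. It would remove participants because their values are high, and so bring selection into the mean.

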4.2. Background Characteristics

4.2.1. Participant Disposition

A disposition table will be provided with the number of study participants for each cohort and overall, in:

- Participants signed informed consent form
- Participants screened
- All Enrolled Set
- FAS
- Safety Analysis Set
- PK Analysis Set
- Immunogenicity Analysis Set

The number and percentage of study participants in each of the following disposition categories will be summarized by cohort and overall. Percentages will be calculated relative to the number of participants in the All Enrolled Set.

- Participants who completed all study intervention
- Participants who completed study
- Participants who met NRTI (TDF/TD) discontinuation criteria
- Participants who met NRTI (TDF/TD) retreatment criteria
- Participants prematurely discontinued VIR-3434
 - Primary reason for premature discontinuation of VIR-3434
- Participants prematurely discontinued VIR-2218
 - Primary reason for premature discontinuation of VIR-2218
- Participants prematurely discontinued PEG-IFN α

- Primary reason for premature discontinuation of PEG-IFN α
- Participants prematurely discontinued TDF/TD
 - Primary reason for premature discontinuation of TDF/TD
- Participants early withdrawal from the study
 - Primary reason for early withdrawal from the study
- Roll over from/to other study/sub-study

A by-participant listing will be provided for the disposition of all participants.

4.2.2. Demographics and Baseline Characteristics

Demographic and baseline characteristics will be summarized by cohort and overall based on the All Enrolled Set using descriptive statistics, including n, mean, SD, median, Q1, Q3, min, and max for continuous variables and numbers and percentages of participants for categorical variables. The number of participants with any missing demographics or baseline characteristics will be summarized for each categorical variable.

Demographic data will be summarized as follows:

- Age at baseline, in years
- Age group (<18, 18 – < 30, 30 – < 40, 40 – < 50, 50 – < 66)
- Sex at birth (Male, Female, Female with child-bearing potential)
- Race (American Indian or Alaska Native, Asian, Black or African American, Native Hawaiian or Other Pacific Islander, White, Multiple, Other)
- Ethnicity (Hispanic or Latino, not Hispanic or Latino, Not Reported, Unknown)
- Country

Baseline characteristics will be summarized as follows:

- Height (cm)
- Weight (kg)
- BMI (kg/m²)

Disease baseline characteristics will be summarized as follows:

- HBeAg status (Positive, Negative)
- Values of HBsAg (IU/mL) and HBsAg (\log_{10} IU/mL)
- HBsAg categories (< 3000 IU/mL, and \geq 3000 IU/mL)
- Values of HBV DNA (IU/mL) and HBV DNA (\log_{10} IU/mL)
- Values of ALT (U/L)

Demographics and baseline characteristics data will be presented in a by-participant listing. In addition, liver elastography results (kPa) and fibrosis/cirrhosis status will also be listed.

4.2.3. Medical History

Medical history will be coded using the Medical Dictionary for Regulatory Activities (MedDRA) version 25.0 or later.

Medical history will be summarized descriptively by system organ class (SOC) and preferred term (PT) by cohort and overall based on the FAS. All medical history data will be presented in a listing.

4.2.4. Prior, Concomitant Medications and Concomitant Procedure

Prior and concomitant medications used will be coded using the World Health Organization Drug Dictionary (WHODD) version Global B3 March 2022 or later and summarized by anatomic therapeutic chemical (ATC) classification level 2, ATC classification level 3, preferred name, and by cohort and overall based on the FAS.

Prior medication: Any medication started prior to administration of the study intervention, regardless of when it ended. If the medication end date is before the date of first dosing of the study intervention, then the medication will be summarized as prior medication, regardless of whether the medication start date is missing or not.

Concomitant medication: Any medication received on or after administration of the study intervention or received prior to administration of the study intervention and continued after administration of the study intervention. If medication start date is on or after administration of the study intervention, then medication will be summarized as concomitant medication regardless of whether the medication end date is missing or not.

Note that any medication that started prior to and continued after administration of the study intervention will be summarized as prior medication and concomitant medication, separately.

If a medication has a completely missing or partially missing start/stop date and it cannot be determined whether it was taken prior to administration of the study intervention, it will be classified as both prior and concomitant medications. Details for handling missing or partial missing dates of medication are described in [Appendix 3](#).

All medications will be provided in a by-participant listing along with a column indicating whether the medication was prior, concomitant, or both. The imputed date will not be presented in the listing.

Concomitant procedure: Any procedure or surgery received on or after administration of the study intervention. The procedure used in this study will be coded using MedDRA version 25.0 or later. All concomitant procedures will be summarized descriptively by SOC and PT, and by cohort and overall based on the FAS.

All concomitant procedures/surgeries will be provided in a by-participant listing.

Missing and/or partial dates of concomitant procedure/surgery will not be imputed.

